#### **6.5.3.3. Exposure to Cytarabine (Consolidation, Intensive Study Only)**

The summary of treatment exposure for cytarabine in the consolidation cycles will include the following information:

- Total number of infusions received;
- Cumulative dose (g/m^2);
- Dose intensity (g/m^2/day).

Cytarabine is administered by intravenous (IV) infusion twice daily for 3 days or follow local prescribing information, in 28 day cycles.

The dose level for cytarabine captured on the CRF is calculated as actual dose administered/BSA (g/m^2). The last available weight of the patient on or prior to the day of dosing will be used.

The cumulative dose (g/m^2) of cytarabine per cycle is the sum of the actual dose levels that the patient received within that cycle (ie, total dose administered (g)/BSA (m^2)). Cumulative dose (g/m^2) of cytarabine is the sum of the actual dose levels that the patient received throughout consolidation.

Since the planned cytarabine dose in consolidation cycles can be 1 or 3 g/m^2 BID according to patient age or different following local clinical practice (eg, Japan will use 2 g/m^2 BID for 5 days in a 28 days cycle), the DI of cytarabine will be calculated for each patient by cycle and across all cycles based on the actual treatment received. The DI (g/m^2) of cytarabine is defined as:

$$\text{DI (g/m}^2\text{/day)} = [\text{cumulative dose (g/m}^2\text{)}] / [\text{number of days with a non-zero dose}].$$

The RDI of cytarabine will not be calculated for consolidation since the intended dose is not captured on the CRF.

#### **6.5.3.4. Exposure to Daunorubicin (Induction Only, Intensive Study Only)**

The summary of treatment exposure for daunorubicin will include the following information:

- Treatment duration (weeks);
- Total number of infusions received;
- Cumulative dose (mg/m^2);
- Dose intensity (mg/m^2/day);

- Relative dose intensity (%).

Daunorubicin is administered by intravenous (IV) infusion daily for 3 days, in 28 day cycles (2 days allowed in re-induction cycle).

The dose level for daunorubicin captured on the CRF is calculated as actual dose administered/BSA ( $\text{mg}/\text{m}^2$ ). The last available weight of the patient on or prior to the day of dosing will be used.

The duration of daunorubicin (in weeks) during the study for a patient is defined as:

$$\text{Treatment duration (weeks)} = (\text{last dose date} - \text{first dose date} + 1)/7.$$

The cumulative dose ( $\text{mg}/\text{m}^2$ ) of daunorubicin per cycle is the sum of the actual dose levels that the patient received within that cycle (ie, total dose administered ( $\text{mg}$ )/BSA ( $\text{m}^2$ )). Cumulative dose ( $\text{mg}/\text{m}^2$ ) of daunorubicin is the sum of the actual dose levels that the patient received throughout induction.

Since the planned daunorubicin dose is 2 (Option 1: ‘5+2’) or 3 (Option 2: ‘7+3’) days in the re-induction cycle, the DI and RDI of daunorubicin will be calculated for each patient by cycle and across all cycles based on the actual treatment received. The DI ( $\text{mg}/\text{m}^2/\text{day}$ ) of daunorubicin is defined as:

$$\text{DI (mg/m}^2/\text{day)} = [\text{cumulative dose (mg/m}^2\text{)}]/[\text{number of days with a non-zero dose}].$$

The RDI of daunorubicin is defined as the actual DI divided by the planned dose per day and expressed in %:

$$\text{RDI (\%)} = 100 \times [\text{DI (mg/ m}^2/\text{day)}]/[60 \times (\text{mg/m}^2/\text{day})].$$

#### **6.5.3.5. Exposure to Azacitidine (Non-intensive Study Only)**

The summary of treatment exposure for azacitidine will include the following information:

- Treatment duration (weeks);
- Total number of injections/infusions received;
- Cumulative dose ( $\text{mg}/\text{m}^2$ );
- Dose intensity ( $\text{mg}/\text{m}^2/\text{day}$ );
- Relative dose intensity (%).

Azacitidine is administered by subcutaneous injection (SC) or intravenous (IV) infusion  $75 \text{ mg}/\text{m}^2$  daily for 7 days, in 28 day cycles.

The dose level for azacitidine captured in the CRF is calculated as actual dose administered/BSA ( $\text{mg}/\text{m}^2$ ). The last available weight of the patient on or prior to the day of dosing will be used.

The duration of azacitidine (in weeks) during the study for a patient is defined as:

$$\text{Treatment duration (weeks)} = (\text{last dose date} - \text{first dose date} + 1)/7.$$

The cumulative dose ( $\text{mg}/\text{m}^2$ ) of azacitidine per cycle is the sum of the actual dose levels that the patient received within that cycle (ie, total dose administered ( $\text{mg}$ )/BSA ( $\text{m}^2$ )).

Cumulative dose ( $\text{mg}/\text{m}^2$ ) of azacitidine is the sum of the actual dose levels that the patient received throughout the study.

The DI) and RDI of azacitidine will be calculated for each patient by cycle and across all cycles. The DI per day ( $\text{mg}/\text{m}^2/\text{day}$ ) of azacitidine is defined as:

$$\text{DI (mg}/\text{m}^2/\text{day}) = [\text{cumulative dose (mg}/\text{m}^2)]/[\text{7 days} \times \text{number of cycles with a non-zero dose}].$$

The RDI of azacitidine is defined as the actual DI divided by the planned dose per day and expressed in %:

$$\text{RDI (\%)} = 100 \times [\text{DI (mg}/\text{m}^2/\text{day})]/[75 (\text{mg}/\text{m}^2/\text{day})].$$

#### **6.5.3.6. Dose Reductions and Interruptions due to Adverse Events**

A dose reduction due to an AE is defined as a non-zero dose where reason for adjustment on the dosing CRF is AE.

The number and percentage of patients with at least one dose reduction as well as a breakdown of dose reductions (1 / 2 /  $\geq 3$ ) and/or the dosage administered will be summarized by treatment and by treatment arm.

An interruption due to an AE is defined as a 0 mg dose administered where reason for adjustment on the dosing CRF is AE. The number and percentage of patients with dose interruptions will be summarized by treatment and by treatment arm. Percentages will be calculated based on the total number of patients in the safety analysis set.

#### **6.5.4. Concomitant Medications and Non-Drug Treatments**

Concomitant medications and non-drug treatments received by patients during the study will be summarized for the safety analysis population by treatment arm.

Concomitant medications refer to all medications which started prior to first dose of study treatment and continued during the on-treatment period (see [Section 3.5](#)) as well as those started during the on-treatment period. Concomitant medications will be coded in the WHO Drug coding dictionary and will be tabulated by Anatomical Therapeutic Chemical (ATC) Classification level 2 and preferred term in descending order of frequency in the glasdegib arm. In case of equal frequency regarding drug class (respectively drug name), alphabetical

order will be used. A patient will be counted only once within a given drug class and within a given drug name, even if he/she received the same medication at different times. Preferred Terms will be reported under each ATC class that it is included under within WHO Drug (no primary path is available in WHO Drug).

Concomitant non-drug treatments refer to all non-drug treatments administered during the on-treatment period. Non-drug treatments will be coded with the most current version of MedDRA and will be summarized by MedDRA's SOC and PT in descending order of frequency in the glasdegib arm. Patients will be counted only once per PT even if he/she received the same treatment multiple times.

Any medications or non-drug treatments which were only administered prior to treatment start will be listed but not summarized.

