### **Post Remission HSCT**

Subjects who are eligible for Post Remission HSCT will undergo HSCT per local standard of care. For HSCT, Day 0 is the first day of HSCT; this is the day when stem cells are infused.

For post remission HSCT, glasdegib or placebo will be interrupted at least 28 days before HSCT and resumed 30-60 days post date of stem cell infusion, once there is ANC engraftment, no  $\geq$  Grade 2 ongoing GVHD, and no ongoing SAEs that prevent resuming glasdegib/placebo in the judgement of the investigator. Confirmed ANC engraftment is defined by ANC  $\geq 0.5 \times 10^9/L$  for 3 consecutive days without growth factor support following HSCT using myeloablative or non-myeloablative conditioning regimen.

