### **5.8. Concomitant Treatment(s)**

All concomitant medications and treatments must be recorded in the CRF except during the HSCT period from the first day of conditioning until a subject resumes glasdegib or placebo post HSCT. During this HSCT period, no concomitant medications (other than transplant conditioning regimen) will be collected. If a patient resumes glasdegib or placebo following HSCT, HSCT-related Medical History must be provided. This will include information regarding ongoing medical conditions and their associated concomitant medications that started from the first day of conditioning until the time of re-starting glasdegib or placebo therapy.

Any prior treatment received within 28 days prior to study entry (including hematopoietic growth factor receptor agonists: erythropoietin, granulocyte colony stimulating factor (G-CSF), romiplostim, eltrombopag) will be recorded in the CRF.

In addition, any transfusion (red blood cells or platelets) within 8 weeks prior to randomization should be recorded in the CRF for the non-intensive study only. Transfusions (red blood cells or platelets) will not be recorded during the HSCT period unless part of ongoing Medical History once they resume glasdegib/placebo.

All prior therapies used to treat AML will be recorded regardless of when they were received by the subject. Information collected will include dates of use, best treatment response and the reasons for stopping therapy.

Every concomitant treatment, blood products, growth factors, as well as interventions, required by the subjects during the active study treatment (and up to 28 days following last study drug administration or until initiation of another anti-cancer treatment) and the reason for its administration must be recorded on the CRF.

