### 3.4. Baseline Variables

The date of first dose (start date) of study treatment is the earliest date of non-zero dosing of any study drug. The date of last dose of study treatment is the latest date of non-zero dosing of any study drug.

No windowing will be applied when defining baseline. Any deviations from the protocol specified window will be documented as protocol deviations.

For efficacy endpoints (except Fatigue) and baseline characteristics the last non-missing assessment prior to randomization will serve as the baseline assessment. For fatigue, similar to other PRO endpoints, the last non-missing measurement on the day of the first dose of study treatment will serve as baseline (note that PRO endpoints are collected prior to study drug dosing on the same day).

For safety (including Eastern Cooperative Oncology Group (ECOG) performance status) the last non-missing assessment performed on or prior to date of the first dose of study treatment (or prior to randomization for patients randomized but not dosed) will serve as the baseline assessment. If there are no observations meeting these criteria, then baseline is considered missing.

For PRO, the measurement, the day of the first dose of study treatment will be used as the baseline measurement. If there are no observations meeting this criteria, then baseline is considered missing.

Triplicate ECGs are collected; therefore the baseline for each ECG measurement is the average of the pre-dose measurements on the baseline day. Unscheduled assessments will not be included in the calculation of the average. The average of the replicate measurements will be determined after the derivation of the individual parameters at each timepoint.

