### 3.5. Safety Endpoints

Safety endpoints will be summarized based on the on-treatment period unless otherwise specified.

On-treatment is defined as the time from the first dose of study treatment to last dose prior to HSCT + 28 days and if applicable, from first dose post-HSCT to last dose + 28 days or start of new anti-cancer drug therapy (minus 1 day), whichever occurs first. Note that conditioning regimens for HSCT (regardless of whether glasdegib is resumed after HSCT) are not considered “new anti-cancer drug therapy”. Adverse events occurring on the same day as the first dose of study treatment will be considered to have occurred during the on-treatment period. All other assessments which occur on the same day as the first dose of study treatment will be considered baseline assessments (see [Section 3.4](#) for the definition of baseline).

Safety data collected outside the on-treatment period as described above will be listed but not summarized.

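### SAP 6.5.4 leaves out of the concomitant-medication table a drug first started between the two on-treatment segments around HSCT, even if it is still taken when blinded therapy resumes

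*SAP*

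**What the plan says.** SAP 6.5.4 defines concomitant medications by start date. Route 1: "Concomitant medications refer to all medications which started prior to first dose of study treatment and continued during the on-treatment period". Route 2: "as well as those started during the on-treatment period".

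Two other SAP sections fix the terms:

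- **First dose.** SAP 3.4: "The date of first dose (start date) of study treatment is the earliest date of non-zero dosing of any study drug". This is one date per patient and cannot be read as the restart after transplant.
- **On-treatment.** SAP 3.5: "On-treatment is defined as the time from the first dose of study treatment to last dose prior to HSCT + 28 days", and then, where it applies, "from first dose post-HSCT to last dose + 28 days" or the day before new anti-cancer drug therapy if that comes first. Transplant conditioning does not count as new anti-cancer therapy.

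The protocol makes a gap between these segments routine. Under Post Remission HSCT, "glasdegib or placebo will be interrupted at least 28 days before HSCT and resumed 30-60 days post date of stem cell infusion". For patients who resume, protocol 5.8 asks for ongoing medical conditions and their "associated concomitant medications that started from the first day of conditioning until the time of re-starting glasdegib or placebo therapy". Protocol 7.1.8 also requires collection of drugs that treat AEs still ongoing from the HSCT period.

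**The concern.** A drug begun in the gap and continued past resumption is taken together with blinded drug, which is what a concomitant-medication table is meant to show. Both routes test when the drug started, and neither asks whether it was being taken on an on-treatment day after the restart. The protocol makes a point of collecting such drugs at resumption, and the SAP then gives them no way into the summary.

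The time around transplant is when new drugs may be started. Protocol 5.8.1 restricts moderate and strong CYP3A4/5 inhibitors, drugs with a known risk of Torsade de pointes and other QT-prolonging drugs during active treatment. A table that drops newly started drugs from this phase understates that co-exposure.

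**Working it through.** The plan states no figure here, so there is none to reproduce. The check applies the two routes to every possible start day.

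**Inputs.** Days are counted from HSCT Day 0, as in the protocol; SAP 5.2.3 calls the same day Day 1.

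- L = day of the last pre-HSCT dose of any study drug (SAP 3.4 and 3.5). In the intensive study L is Day -28 or earlier, since protocol Table 7 interrupts all study therapy at least 28 days before HSCT.
- R = day of the first post-HSCT dose, Day 30 to Day 60 (protocol, Post Remission HSCT).
- The drug has a known start date and is still taken after R.

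**Segments.** Segment 1 ends on Day L + 28. Segment 2 starts on Day R. The uncovered start days run from L + 29 to R - 1, which is R - L - 29 days.

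**Routes for a drug started on one of those days.**

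- Route 1 fails: the drug started after the earliest dose of any study drug.
- Route 2 fails: its start date lies in neither segment.

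**Results.**

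| L | R | Uncovered start days | Number (R - L - 29) |
|---|---|---|---|
| -28 | 30 | 1 to 29 | 30 + 28 - 29 = 29 |
| -28 | 60 | 1 to 59 | 60 + 28 - 29 = 59 |
| -29 | 30 | 0 to 29 | 30 + 29 - 29 = 30 |
| -29 | 60 | 0 to 59 | 60 + 29 - 29 = 60 |
| -35 | 30 | -6 to 29 | 30 + 35 - 29 = 36 |
| -35 | 60 | -6 to 59 | 60 + 35 - 29 = 66 |
| -8 | 30 | 21 to 29 | 30 + 8 - 29 = 9 |
| -8 | 60 | 21 to 59 | 60 + 8 - 29 = 39 |

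The last two rows are for the non-intensive study. There the 28-day interruption applies to glasdegib or placebo, while protocol section 3 lets azacitidine continue before HSCT. Because SAP 3.4 counts any study drug, L can be later than Day -28. Day -8 is an assumed example.

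**Comparison with neighbouring rules.**

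- *Non-drug treatments, also in SAP 6.5.4*, are those administered during the on-treatment period. That is an overlap test, so a non-drug treatment given on both sides of the restart is kept and a drug in the same position is not.
- *Missing dates, SAP 5.3.1*: a drug with a wholly missing start date counts as concomitant, and a partial date not clearly before first dose is handled in a similar worst-case way. A drug correctly dated to the gap is excluded; the same drug with no start date is included.

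**The case against.** The case for leaving this alone has several parts.

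**The intent is clear.** SAP 6.5.4 opens by covering medications received during the study, and sends to listings only those given solely before treatment start. A drug continued past resumption is not in that group. This suggests a drafting slip rather than a deliberate exclusion, but the programmed rule is the two-route definition, and that definition excludes the drug.

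**Listings remain.** SAP 3.5 says "Safety data collected outside the on-treatment period as described above will be listed but not summarized". That keeps the record visible but does not put it in the table. The exposure itself falls inside segment 2; only the start date falls outside.

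**Not every drug started around HSCT is lost.** A reader might infer that, and the documents do not support it:

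- A patient is counted once per drug name, so a drug also taken at another on-treatment time still appears. Protocol 5.8.2 encourages or expects antimicrobials and anti-emetics during chemotherapy, so some relevant drugs may already be tabulated for the same patient.
- Drugs started after conditioning but within 28 days of the last pre-HSCT dose are counted.
- Drugs with missing start dates are counted.

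**The protocol does not collect exactly the excluded set.** Protocol 5.8 collects drugs tied to ongoing conditions in patients who resume, in a window that opens on the first day of conditioning. Protocol 7.1.8 adds drugs for ongoing AEs. Otherwise no concomitant medications are collected in the HSCT period. The SAP gap opens on a different day, so the two sets overlap without coinciding.

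**AE and QTc findings after HSCT are not made uninterpretable.** A reader might infer that too. The table is by arm, drug class and preferred term, is not split by HSCT phase, and could not show post-transplant co-medication separately even with a corrected definition. The visible ECG analyses do not use concomitant medications.

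These points limit the size of the problem. None of them brings a new, gap-started drug with a known date into the table.

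**Conclusion.** The definition is wrong as written, within narrow limits. It leaves out a medication that is new to the patient, has a known start date between the two on-treatment segments, and is still taken when study drug resumes. In the intensive study at least 29 start days are uncovered for a patient resuming on Day 30, and at least 59 for one resuming on Day 60. In the non-intensive study the gap can be shorter.

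The number of patients affected cannot be derived, because the documents give neither transplant nor resumption rates. A reader might multiply assumed rates, such as 20-50% of 400 transplanted and 30-70% of those resuming, to get 400 x 0.20 x 0.30 = 24 up to 400 x 0.50 x 0.70 = 140. That would count assumed resumers. To be affected, a patient must also have a new drug that was started in the gap, collected, dated and continued.

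The consequence is under-counting of post-transplant co-medication in one descriptive safety table. OS, error rates, and the AE and ECG analyses are unaffected.

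**What to change.** Replace the two routes in SAP 6.5.4 with an overlap rule: a medication is concomitant if it was taken on at least one day of the on-treatment period. In programming terms, its start date is on or before the last day of an on-treatment segment, and its stop date is on or after the first day of that segment or it is ongoing. State explicitly that this includes drugs started between the two segments and ongoing at the first post-HSCT dose. Drugs both started and stopped in the gap would stay out, as they should.

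This matches the wording the section already uses for non-drug treatments. The cost is one SAP sentence and one programming condition. It needs no new data collection, although the added records will be limited to what protocol 5.8 and 7.1.8 collect. Sample size, power and alpha do not change.

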#### **6.5.5. Prior and Subsequent Anti-Cancer Therapies/Procedures**

Prior and subsequent Anti-Cancer Therapies and Procedures are defined as therapies entered on the 'Prior Cancer Therapy' and 'Follow-up Cancer Therapy' CRF pages, respectively. The number and percentage of patients within each category (medication therapy, radiation therapy, and surgeries) will be provided by treatment arm.

Medications will be coded using the WHO Drug coding dictionary and will be tabulated by preferred term in descending order of frequency on the glasdegib arm.

Analyses will be based on the FA set by treatment arm.

### **6.6. Safety Summaries and Analyses**

Unless otherwise specified, summaries of AEs and other safety parameters will be based on the safety analysis population by treatment arm.

#### **6.6.1. Adverse Events**

All analyses will be based on treatment emergent events unless otherwise specified. Treatment emergent is defined in [Section 3.5.1](#).

A high level summary of adverse events will include the number and percent of patients with:

- Any Adverse Event;
- Serious AE;
- Adverse Events with maximum CTCAE Grade 3-4;
- Grade 5 events;
- AEs leading to dose interruptions separately for each study drug, for chemotherapy, and for any study treatment;

- AEs leading to dose reductions separately for each study drug, for chemotherapy, and for any study treatment;
- AEs leading to withdrawal separately for each study drug, for chemotherapy, and for any study treatment.

Additionally, the number of events reported for each of the categories above will be provided. Each unique adverse event at the PT level in each treatment arm of the study for a patient is included in the count.

Seriousness, toxicity grade, action taken (interruption, reduction, and withdraw) are as reported by the investigator on the adverse event CRF.

Summaries by treatment arm, SOC and PT in decreasing frequency based on the frequencies observed in the glasdegib arm will be provided for:

- Treatment Emergent Events by Maximum Toxicity Grade (All Causality);
- Treatment Emergent Events by Maximum Toxicity Grade (Treatment Related);
- Serious Treatment Emergent Events by Maximum Toxicity Grade (All Causality);
- Serious Treatment Emergent Events by Maximum Toxicity Grade (Treatment Related).

An event will be considered treatment related if the investigator considered the event related to the study drug or this information is unknown.

The above four summaries will also be provided separately for (1) treatment emergent events prior to HSCT, (2) non-treatment emergent events during HSCT, and (3) treatment emergent events after HSCT.

The following summaries will be provided by treatment arm and PT (ie, summaries will not include SOC) in decreasing frequency based on the frequencies observed in the glasdegib arm for:

- Treatment Emergent Events (All Causality) Experienced by  $\geq 10\%$  of patients in either treatment arm;
- Treatment Emergent Events (All Causality) by Preferred Term and Maximum Toxicity Grade;
- Treatment Emergent Grade 3-5 Events (All Causality) by Preferred Term and Maximum Toxicity Grade;
- Treatment Emergent Adverse Events Leading to Dose Interruptions by Maximum Toxicity Grade (All Causality) separately for each study drug, for chemotherapy, and for any study treatment;

- Treatment Emergent Adverse Events Leading to Dose Reductions by Maximum Toxicity Grade (All Causality) separately for each study drug, for chemotherapy, and for any study treatment;
- Treatment Emergent Adverse Events Leading to Permanent Withdrawal by Maximum Toxicity Grade (All Causality) separately for each study drug, for chemotherapy, and for any study treatment;
- Serious Treatment Emergent Events (All Causality).

Each patient will be counted only once within each PT.

As described in [Section 5.3.2](#), in case a patient has events with missing and non-missing toxicity grades, the maximum of the non-missing grade will be displayed. Missing grade will only be displayed in the event that only one event has been reported for a patient and the grade is missing.

